9 STUDY OVERSIGHT

The PI will be responsible for study oversight, including monitoring safety, ensuring that the study is conducted according to the protocol and ensuring data integrity. The NCC will provide the PI with current data summaries, and the PI will review the data for safety concerns and data trends at regular intervals, and will promptly submit reportable events to the IRB and NIDCR that arise during the conduct of the study, per the IRB's reporting time-frame requirements. To ensure data integrity, the PI, NCC, and study team will adhere to data quality management processes (please see Section 13).

10 CLINICAL SITE MONITORING

No outside clinical site monitoring will be employed for this study. The NCC is responsible for launching the study and collecting data received as part of the study. Quality Assurance/Quality Control activities associated with data collection and processing will be outlined in the Data Management Plan. The NCC will ensure that the quality and integrity of the study data and data collection are maintained. The NIDCR reserves the right to conduct independent clinical site monitoring as necessary.

11 STATISTICAL CONSIDERATIONS

11.1 Study Hypotheses

This is a cross-sectional questionnaire of Network dentists assessing their treatment practices regarding the management of adults with IADD. The primary objective will test the hypothesis that a lower proportion of dentists in private practice treat patients with IADD than dentists in other practice types. The secondary objective will provide descriptive data. As such, formal hypothesis testing will not be conducted to achieve the secondary objectives.

11.2 Sample Size Considerations

11.1 Considerations

The primary objective of the study is descriptive (i.e., to understand the proportion of dentists in different practice types that treat adults with IADD). As such, sample size calculations are based on the precision with which we can estimate confidence interval widths. To a good approximation, if W is the width of the 95% confidence interval (i.e., the confidence interval is of the form $P \pm W/2$) for an estimated proportion P based on a simple random sample of N observations, then the N needed to achieve that width is given by

$$N \cong 16 * P * (1 - P) / (W^2),$$

where P and W are expressed on a fractional basis. Thus, a proportion of 20% corresponds to $P=0.20$, and if the width of the confidence interval were 10 percentage points, then W would be 0.10. For a given value of W , the formula above is symmetric about $P=0.5$ and is largest for $P=0.5$. Hence using $P=0.5$ above will give a conservative value of N that assures a width $\leq W$ regardless of the value of P .

Similarly, the above formula can be used to solve for the precision of a CI given the sample size. In this case we get

$$W \cong 4 * \text{SQRT}\{P * (1 - P) / N\}.$$

For the overall population estimate, or indeed any estimate not restricted to one of the two practice strata used for sampling, the above formulas will be biased in that they do not account for the impact of variability introduced by the sampling. Nonetheless they should serve as a good ballpark estimates. For those estimates that are limited to one of the practice strata used for sampling, the above formulas should be unbiased.

Table 1 shows the precision (in this case expressed as $W/2$, or the half-width of a 95% confidence interval) for various combinations of N and P . Thus, the

corresponding intervals would be of the form $P \pm W/2$. Since the results will be symmetric about $P=0.5$, we only present results for $P \leq 0.5$. The calculations for $N=500$ correspond to prevalence estimates for the sample as a whole, and as noted above may be somewhat inaccurate since they do not account for the stratified sampling. The other calculations reflect potential sample sizes for the various practice types and are not affected by the sampling. We assume these subgroup sample sizes may vary anywhere from 50 to 150. To interpret the table, consider an N of 100 and a prevalence of 0.4. Per the table, we would estimate the true proportion with 95% CI $P \pm .096$. In the worst case shown in the table (group size of 50 and a prevalence of .5), the 95% CI would be of the form $P \pm .139$.

Table 1. Size of half width of 95% CI for simple proportion.

true prevalence	N				
	50	75	100	150	500
0.10	0.083	0.068	0.059	0.048	0.026
0.15	0.099	0.081	0.070	0.057	0.031
0.20	0.111	0.091	0.078	0.064	0.035
0.25	0.120	0.098	0.085	0.069	0.038
0.30	0.127	0.104	0.090	0.073	0.040
0.35	0.132	0.108	0.093	0.076	0.042
0.40	0.136	0.111	0.096	0.078	0.043
0.45	0.138	0.113	0.098	0.080	0.044
0.50	0.139	0.113	0.098	0.080	0.044

calculations assume simple random sampling

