4 STUDY DESIGN

This study is a cross-sectional questionnaire of Network dentists practicing all practice types that are represented in the Network. Responses to the questionnaire will be analyzed by the type of practice setting of the respondent.

Recruitment will be stratified by practice setting, with the goal of obtaining approximately equal numbers of providers from (1) all private practices via random sample and (2) all other practice types of whom all will be invited to participate, with a total respondent sample size of approximately 500-550.

Eligible Network dentists as described in the previous paragraph will be sent an email invitation to participate in the questionnaire study. The questionnaire will take approximately 15 minutes to complete and will be administered using the Electronic Data Capture System (EDC) on the Network HUB website, housed at the Network Coordinating Center (NCC).

Following the launch of the questionnaire, approximately 40 of the initial survey responders will be selected to complete the electronic questionnaire again (approximately 2 weeks post initial questionnaire completion) to establish test-retest reliability.

Approximately 3 months are estimated to complete recruitment into the study to obtain the desired sample size.

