5.2 Strategies for Recruitment and Retention

Recruitment

As of September 2021, 7,748 members were enrolled in the National Dental PBRN. Of this total, approximately 34% are dentists providing care in private practices of any size, including managed care organizations, and approximately 8% are dentists providing care in community health centers, academic dental centers, hospitals, corporate offices, and other practice types. We will actively recruit new dentists from public health clinics, community health centers and academic dental centers to join the Network via, as practitioners within these practice types are underrepresented in the Network, as well as are more likely to treat patients with IADD.

Dentists will be recruited from the following two strata: private practices dentists; and all other Network dentists. Sampling fractions will be determined based on the number of dentists in these two strata at the time of recruitment, with the goal of obtaining roughly equal numbers of dentists in each stratum if possible. Based on current numbers and assuming a response rate of 50%, we anticipate contacting approximately 20% of private practice dentists and 100% of other dentists, with projected enrollment for the two strata of approximately equal numbers participants per each group.

Dentists will be contacted via e-mail with a link to a web-based questionnaire. Those who do not respond will be sent e-mail reminders once a week for two weeks following initial contact. If no response after the two e-mail reminders, National Dental PBRN

Node Coordinators (NCs) will engage in recruitment, contacting individuals who have not completed the questionnaire. Meetings will be held as needed with Regional NCs to review recruitment issues and enrollment progress. NCs will prioritize follow up with non-private practice practitioners to promote equal sampling from each practice type to maximize the generalizability of the sample, recruitment efforts may continue beyond a sample of approximately 500-550 respondents.

Compensation

Participants who wish to receive compensation and are able to accept payment will be remunerated \$50 for completing the electronic questionnaire. If participants complete the test-retest of the electronic questionnaire, they will be remunerated an additional \$50. Payment will be sent to participants following the conclusion of each of the waves of the study.

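### Table 1's N=500 column gives simple-random-sample precision for the overall estimate; the planned strata and equal split give about ±0.052 at P=0.5, not ±0.044

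*Protocol*

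**What the plan says.** Recruitment uses two strata, private practice and everyone else. Section 5.2 puts them at about 34% and 8% of 7,748 Network members. Assuming a 50% response, it says "we anticipate contacting approximately 20% of private practice dentists and 100% of other dentists", with roughly equal numbers of respondents per stratum as the goal. Section 4 sets the total: "with a total respondent sample size of approximately 500-550".

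The sample size rests on precision alone. Table 1 is titled "Size of half width of 95% CI for simple proportion" and its footnote reads "calculations assume simple random sampling". The text explains the last column: "The calculations for $N=500$ correspond to prevalence estimates for the sample as a whole". For that column the protocol admits that the formulas are biased because they leave out variability introduced by the sampling, and that the figures "correspond to prevalence estimates for the sample as a whole, and as noted above may be somewhat inaccurate since they do not account for" stratification. It then reassures the reader: "Nonetheless they should serve as a good ballpark estimates".

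The Final Analysis Plan (also numbered 11.2) commits every calculation to adjust for the stratified sampling, so that estimates are unbiased and intervals accurate.

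**The concern.** The overall Network proportion is the first item in the primary objective, and Table 1 gives the only numerical precision stated for it. The smaller stratum is deliberately over-represented: about 19% of the dentists in the two strata are to supply about half of the respondents. Weighting back to the Network, as the analysis plan requires, normally costs precision. The interval behind the sample size is therefore not the interval the analysis will report.

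The caveat in the text does not settle this. A reader told only that the figures are somewhat inaccurate cannot tell how large the inaccuracy is, and might suppose that stratification helps, as it often does under proportional allocation. The protocol also says of its formula: "Hence using $P=0.5$ above will give a conservative value of N that assures a width" no greater than W whatever the prevalence. For the overall estimate under this allocation, that assurance does not hold.

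**Working it through.** **Inputs.** Stratum shares 34% and 8% of 7,748, contact fractions 20% and 100%, 50% response, and the equal-numbers goal (all Section 5.2); N=500 (Table 1); two-sided 95%, z = 1.96.

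**1. The printed figure.** 1.96 × √(0.5 × 0.5 / 500) = 0.0438, which is the printed 0.044. All 45 cells of Table 1 reproduce in this way, as simple random samples.

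**2. Weights.** Private 0.34 × 7,748 ≈ 2,634; other 0.08 × 7,748 ≈ 620. W₁ = 34/42 = 0.8095 and W₂ = 8/42 = 0.1905. Squares: 0.6553 and 0.0363, sum 0.6916.

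**3. Stratified half-width.** h = 1.96 × √(Σ W_h² P_h(1−P_h)/n_h). With n = 250/250 and P = 0.5 in both strata: 1.96 × √(0.25/250 × 0.6916) = 0.0515. The design effect is 2 × 0.6916 = 1.38, the effective N is 500/1.383 ≈ 361, and the width ratio is √1.383 = 1.18.

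**4. The column under the same assumptions (250/250, equal prevalence).**

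| P | Table 1 | Stratified |
|---|---|---|
| 0.10 | 0.026 | 0.031 |
| 0.20 | 0.035 | 0.041 |
| 0.30 | 0.040 | 0.047 |
| 0.40 | 0.043 | 0.051 |
| 0.50 | 0.044 | 0.052 |

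**5. Other allocations, P = 0.5.**
- Literal contact fractions: 2,634 × 0.2 × 0.5 ≈ 263 and 620 × 0.5 = 310, total 573. Half-width 0.050, against 0.041 for a simple random sample of 573.
- Equal split of 550 (275/275): 0.049, against 0.042.

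**6. Unequal prevalence (assumed values, private/other, 250/250).** The comparator is 1.96 × √(P(1−P)/500) with P = W₁P₁ + W₂P₂.

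| Private/other | Stratified | Simple random | Ratio |
|---|---|---|---|
| 0.4/0.7 | 0.0503 | 0.0437 | 1.15 |
| 0.7/0.9 | 0.0465 | 0.0385 | 1.21 |
| 0.1/0.3 | 0.0320 | 0.0302 | 1.06 |
| 0.1/0.5 | 0.0323 | 0.0334 | 0.97 |

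**7. Finite-population correction.** With factors 1 − 250/2,634 and 1 − 250/620, the 250/250 half-width at P = 0.5 is 0.0486. A simple random sample of 500 from 3,254 with the same correction gives about 0.040, so the relative loss stays near 20%.

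**8. Subgroups that cut across strata.** With equal stratum totals, respondents' weights are in the ratio 34:8. If a share r of a subgroup's respondents is private and prevalence is equal, the design effect is (34²r + 8²(1−r)) / (34r + 8(1−r))². This gives 1.06 at r = 0.9, 1.38 at r = 0.5, 1.54 at r = 0.1, a maximum of about 1.62 near r = 0.19, and 1.0 when the subgroup lies in one stratum.

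**The case against.** The strongest reply is that nothing is hidden or miscalculated. Table 1 is correct for what its footnote says it is. The bias is admitted for any estimate not confined to one stratum, which covers location and specialty, and the mention of unaccounted variability hints at the direction. The final analysis already uses design-adjusted intervals. The protocol sets no target width for the overall estimate, so no decision turns on the difference. All of this stands, and it limits the point to an understated and unquantified precision statement. It does not make the column right: the size can be calculated from Section 5.2, and calling the result a good ballpark gives reassurance that has not been checked.

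Some stronger readings are tempting, but the document does not support them:

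- *The column always errs on the favourable side.* It does not. Section 11.1 hypothesises lower prevalence in private practice, and with 0.1 against 0.5 the simple formula is slightly conservative.
- *The 0.052 follows from the stated contact fractions.* It follows from the equal-numbers goal at N=500. The fractions themselves lead to 573 respondents and 0.050.
- *Location and specialty estimates carry the same design effect of about 1.4.* The effect depends on each subgroup's stratum mix, which the protocol does not give.
- *The study is too small.* With no required width for the overall estimate, this cannot be inferred.

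The weights are also provisional. The 34% and 8% shares precede the eligibility criteria and the planned recruitment of non-private dentists, and sampling fractions are to be set at recruitment. A larger second stratum would reduce the loss.

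**Conclusion.** The point holds in limited form. For the overall Network estimate, Table 1's N=500 column is not the precision that the planned design-adjusted analysis would deliver at P=0.5, the value the protocol itself treats as conservative. Under weights of 0.81/0.19, 250 respondents per stratum, equal prevalence and no finite-population correction, intervals are 18% wider than printed. Relaxing the equal-prevalence assumption moves the ratio between 0.97 and 1.21 in the cases checked, so the understatement is usual but not universal. With the finite-population correction, the 250/250 value of about 0.049 still exceeds the printed 0.044. Precision for estimates within one stratum and the planned analysis are sound. This is a correction to the stated precision and not a flaw in the design.

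**What to change.** - Replace the N=500 column with 1.96 × √(Σ W_h² P_h(1−P_h)/n_h). State the assumed weights (0.81/0.19), the 250/250 split and equal prevalence, giving 0.031 at P=0.10 up to 0.052 at P=0.50. Note that the weights will be updated at recruitment.
- Replace the ballpark sentence with a statement that the simple-random-sample formula usually understates the width for the overall estimate, by about 18% under these assumptions, and that the difference varies with the stratum prevalences.
- For location and specialty subgroups that span both strata, say that the design effect depends on the subgroup's stratum mix, from 1.0 to about 1.6 at equal prevalence. Do not quote a single value.

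The cost is one table column and two or three sentences. The stated precision becomes somewhat less favourable; no more respondents are needed and the analysis does not change.

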11.2 Final Analysis Plan

Primary Objective: The primary objective is to determine the proportion of participating Network dentists' who provide care for adults with IADD with various behavior tolerances for dental care, both within the network overall and also by practice type, location, and specialty. All calculations will adjust for the stratified nature of the sampling in order to provide unbiased estimates and accurate confidence intervals. For both the population as a whole and the various subgroups of interest, we will calculate both estimated prevalences and their corresponding 95% confidence intervals. Secondary analyses will use logistic regression models to assess factors that are associated with the treatment of these patients.

Secondary Objective: Additional secondary outcomes are to determine attitudes, perspectives, and rationale why dentists treat patients with IADD or not, as well as the methods, processes, and procedures participating Network dentists utilize to provide care for adults with IADD. These analyses will be exploratory in nature, and will include a mix of simple descriptive statistics as well as various regression models.

Additionally, these data will be evaluated to determine the feasibility of the development of a training protocol for methods or procedures to encourage dentists to manage and treat adults with IADD more broadly.

Missing data. Data from incomplete questionnaires may be included in data analyses. Depending on the extent of missing data and available resources for analyses, the study team may consider statistically appropriate methods for imputing missing information.

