6.2 Phase 2, Part A – Recruitment of Practitioners into the Study

Eligible dentists will be identified from responses to the Network Enrollment Questionnaire and will be invited to participate based on inclusion criteria.

A random sample of eligible dentists in the Network from the private practices will be taken, and all dentists from other practice types will be invited to participate.

Agreement to complete the questionnaire will indicate that study participants have read the consent information, and this will imply tacit consent. A waiver of signed consent will be requested from the IRB.

Phase 2, Part B– Retest of the Questionnaire

Dentists selected from among those study participants who completed the questionnaire will be emailed a second online questionnaire request approximately two weeks after the receipt of their first completed questionnaire.

Dentists will be informed they have approximately one week to respond to the invitation to complete the retest. If the retest is not completed within the approximate one-week time frame, the link to the retest questionnaire will be disabled. A new potential retest participant will be selected from those having already completed the questionnaire until a total of approximately 40 retests have been completed.

Completion of the retest questionnaire will indicate implied consent.

Phase 3 – Merging Study Questionnaire with Enrollment Questionnaire and Completion of Data Analyses

Study questionnaire and Network enrollment questionnaire data will be linked using participant IDs.

Contact information will be removed from the final merged dataset and data will be stored/saved using Unique Participant IDs.

Data Analyses will be completed as described in Section 11.3 Final Analysis Plan.

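### Adjusting for the two sampling strata cannot by itself give unbiased estimates and accurate intervals at a planned 50% response

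*Protocol*

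**What the plan says.** The statement at issue is in the Final Analysis Plan (headed 11.2 in the text, 11.3 in the contents list): "All calculations will adjust for the stratified nature of the sampling in order to provide unbiased estimates and accurate confidence intervals". The same paragraph aims at the whole network population as well as subgroups.

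Section 5.2 gives the sampling plan. It starts "Based on current numbers and assuming a response rate of 50" per cent, and continues: "we anticipate contacting approximately 20% of private practice dentists and 100% of other dentists". The non-private stratum pools community health centers, academic centers, hospitals, corporate offices and others.

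Non-response is addressed in the field: two e-mail reminders, then coordinator contact, with $50 for completion (Sections 5.2 and 7). A dentist who still does not answer is taken to be uninterested (Section 7). The missing-data paragraph deals with partly completed questionnaires and makes imputation optional.

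Eligibility is read from the Network Enrollment Questionnaire (Sections 5.1 and 6.2), so enrollment data exist for every invitee. The analytic use stated for them is linkage: "Study questionnaire and Network enrollment questionnaire data will be linked using participant IDs".

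**The concern.** Stratum weights undo the over-sampling of non-private dentists. If they are built from achieved respondents, they also absorb a difference in response rate between the two strata. They do nothing about who responds within a stratum. With half the invitees expected to be silent, unbiasedness needs a further condition: within each stratum, treaters and non-treaters of adults with IADD respond at the same rate.

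The protocol's own text makes that condition doubtful. Sections 5.2 and 6.1 expect dentists in public health clinics, community health centers, hospitals and academic settings to see more of these patients. Several of these settings share the non-private stratum with corporate offices and other types. If response differs among them, the stratum estimate shifts, and a two-stratum weight cannot detect it.

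The primary result is a proportion, so such selection enters it directly, and the reported interval carries no trace of it.

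**Working it through.** **1. The plan's own precision figure.** Table 1 at N=500, P=0.5: 1.96 × √(0.5 × 0.5 / 500) = 0.0438, printed as 0.044. All 45 cells reproduce to rounding with 1.96 (largest deviation 0.0005).

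**2. Expected numbers (Section 5.2), before eligibility exclusions and new Network members.**
- Private: 7,748 × 34% = 2,634; × 20% = 527 invited; × 50% = 263 respondents.
- Other: 7,748 × 8% = 620; all invited; × 50% = 310 respondents.
- Total: about 1,147 invited and 573 respondents, roughly in line with the 500-550 target. About 573 invitees would have enrollment data and no answer.

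**3. What stratum weighting does.** Population shares are 2,634/3,254 = 0.81 and 0.19. The half-width at P=0.5 is 1.96 × √(0.81² × 0.25/263 + 0.19² × 0.25/310) = 0.050. The same formula gives 0.030, 0.040 and 0.046 at P = 0.10, 0.20 and 0.30. No finite-population correction is applied. This step handles sampling fractions only.

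**4. The condition for unbiasedness.** Within a stratum, if treaters respond at rate r1 and non-treaters at r0, the respondents' proportion is on average P·r1 / (P·r1 + (1−P)·r0). It equals P only when r1 = r0.

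**5. Illustration.** The documents give no response rates by outcome. Assume r1 = 0.55 and r0 = 0.45 in both strata; only the ratio matters.

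| True P | Expected estimate | Shift (points) | Table 1 half-width, N=500 | Stratum-weighted half-width |
|---|---|---|---|---|
| 0.10 | 0.055/0.460 = 0.120 | +2.0 | 2.6 | 3.0 |
| 0.20 | 0.110/0.470 = 0.234 | +3.4 | 3.5 | 4.0 |
| 0.30 | 0.165/0.480 = 0.344 | +4.4 | 4.0 | 4.6 |
| 0.50 | 0.275/0.500 = 0.550 | +5.0 | 4.4 | 5.0 |

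A wider assumed split of 60%/40% gives 0.391 at P=0.30 and 0.600 at P=0.50. Swapping the two rates reverses the sign.

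**6. Effect on coverage.** At P=0.50 with the 55/45 split, 55% of respondents and 45% of non-respondents are treaters. The bias is (1 − 0.5) × 10 = 5 points. Coverage is Φ(1.96 − b/se) − Φ(−1.96 − b/se). With se = 0.0224 (simple random sample of 500) it is about 39%; with the stratum-weighted se = 0.0255 it is about 50%.

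**7. What enrollment data could recover (invented example).** Within one stratum, class A holds 30% of dentists, with 70% response and 60% treating. Class B holds 70%, with 41.4% response and 40% treating. The true value is 0.3 × 0.6 + 0.7 × 0.4 = 0.460. The respondents give (0.3 × 0.7 × 0.6 + 0.7 × 0.414 × 0.4)/0.5 = 0.484. Weighting by class returns 0.460, because here response depends only on the class.

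**The case against.** **The sentence concerns the sampling design only.** The sample-size section uses biased and unbiased in a narrow design sense, and the Final Analysis Plan can be read that way too. That makes the slip one of scope. But the sentence promises unbiased estimates and accurate intervals for the population, and stratum adjustment does not deliver these at 50% response unless the unstated condition holds.

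**Non-response weighting belongs in an analysis plan.** Section 15.3 refers report content to a statistical procedure document that is not shown. A reader might infer that the enrollment data on non-respondents will go unused. The protocol cannot prove that, and the point does not depend on it.

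**Fieldwork mitigates.** Reminders, coordinator calls and payment may bring in dentists with no interest in the topic. They may reduce selection, but the plan still expects 50% response after them.

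**The stated target is participating dentists.** The same objective also covers the network overall, so this wording does not remove the problem.

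**Enrollment weighting cannot remove selection on the outcome itself.** This stands. No enrollment item on treating IADD patients is described, so the recoverable share is unknown.

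**Availability.** Section 5.1 ties participation level, percent child patients and weekly visits to enrollment items, and the protocol summary does so for practice type. Completeness of specialty and location for every invitee is not shown.

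**Conclusion.** The point holds as a correction to a stated claim. Stratum adjustment alone gives unbiased estimates at 50% response only if response within each stratum is unrelated to treating adults with IADD. The protocol does not state this and gives reason to doubt it.

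Three stronger readings are not supported:
- **That the primary estimate will be too high by a known amount.** Neither size nor direction can be derived. All the shifts shown rest on assumed response rates.
- **That a modest response difference generally exceeds the sampling error.** Under the 55/45 split the shift stays below the Table 1 half-width at a true 10%, 15% (+2.7 against 3.1) and 20%. Against the stratum-weighted half-width it is smaller at 30% and only equal at 50%.
- **That the contrast between private and other dentists is biased merely because their response rates differ, for example through the prioritised follow-up of non-private dentists.** If response is unrelated to treating within each stratum, both proportions and their difference remain unbiased. Similar selection in both strata would partly cancel in the difference.

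The change is worth making because the data for a better estimate are already held.

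**What to change.** - Limit the sentence to saying that stratum weights correct for the unequal sampling fractions.
- Add a non-response adjustment within each stratum: weighting classes, response propensity, or raking to the invited frame. Use enrollment variables held for all invitees, such as detailed practice type, participation level, percent child patients and weekly visits, plus specialty and location where available.
- Keep the enrollment records of all invitees for this purpose. Check that the consent arrangement in Section 14.3, where consent is given on entering the questionnaire, allows use of non-respondents' records.
- Report the design-weighted and the non-response-adjusted estimates side by side.
- State that selection on the outcome not explained by enrollment variables remains.

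Cost: slightly wider intervals from more variable weights and a little more analysis work. No new data collection is needed.
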